3.3.4 Hypertension

Subjects will be asked to monitor their blood pressure at home at least once a day and contact the UOB team for elevated readings. However, elevated BP readings should be confirmed by a qualified health care professional and decisions regarding grading of hypertension and initiation/intensification of antihypertensive therapy will be driven by BP measurements performed by a health care professional. Table 1 outlines the management plan for patients developing hypertension on therapy. Although CTCAE criteria will be used to grade hypertension, the scheme outlined in Table 1 will be used to guide dose modifications. Early treatment of grades 1-2 hypertension to prevent or minimize the risk of developing more persistent or clinically significant hypertension is allowed and is not considered a grade 3 event.

Agents typically used to treat hypertension include calcium channel blockers such as amlodipine (agents such as verapamil or diltiazem, which are potent inhibitors of CYP3A4 should be avoided where possible, as should agents in this category that have the potential to prolong QTc), diuretics, ACE inhibitor, beta-blockers and angiotensin receptor antagonists. The choice of agents and dosage used may vary based on individual circumstances.

Table 1

	BP Measurements - Systolic/Diastolic	Treatment/Dose Modification
A	>150 mmHg (systolic) OR >100 mmHg (diastolic) OR Increase of diastolic BP by ≥ 20 mmHg regardless of baseline BP	
 • Add new or additional antihypertensive medications or increase dose of existing medications. • Maintain dose of ZD6474. • If unable to control BP to <150/100 in two weeks, hold ZD6474 and follow guidelines under row C
B	>180 mmHg (systolic) OR >110 mmHg (diastolic) OR Symptomatic	
 • Hold ZD6474. • Add new or additional antihypertensive medications or increase dose of existing medications. • Resume treatment at same dose level when BP falls to <140/90 or baseline.
C	>150 mmHg (systolic) OR >100 mmHg (diastolic) Despite therapy for at least 2 weeks	
 • Hold ZD6474. • Maintain or intensify antihypertensive therapy • Resume treatment at one lower dose level when BP falls to <140/90 or baseline
D	CTCAE Grade 4	
 • Discontinue ZD647 • No further treatment with ZD 6474 allowed except in patients benefiting from therapy in whom ZD6474 may be restarted at one lower dose level if BP is controlled to <140/90 within 3 weeks and there are no permanent sequelae. Patient will be removed from study if a second episode of grade 4 hypertension occurs

3.3.5 Other Toxicity

If any other CTCAE grade 3 or 4 non hematologic toxicity attributable to ZD6474 develops (not outlined in Section 3.3.1-3.3.4), study treatment should be interrupted until the toxicity resolves to less than or equal to CTCAE grade 1 or baseline. At the time of resolution, patients with grade 3 toxicity may resume study treatment at one dose level lower. Patients with grade 4 nonhematologic toxicity will discontinue ZD6474 and be taken off study. Patients with grade 3 or 4 neutropenia or thrombocytopenia attributable to ZD6474 will have their therapy interrupted until resolution to less than or equal to CTCAE grade 1 or baseline, at which point treatment may be resumed at one dose level lower. If study treatment must be interrupted for more than 3 weeks to allow for toxicity to resolve, the subject's participation in the study will be discontinued. Dose reductions or study drug interruptions will not be made for laboratory abnormalities not considered clinically significant, regardless of grade.

3.4 RESEARCH STUDIES

Sample acquisition and planned studies

Blood samples for evaluation of basal plasma levels of angiogenesis biomarkers such as VEGF and to assess the effect of ZD6474 on these biomarkers will be obtained on study entry and at each clinic visit. 5-10 cc of venous blood will be collected into lavender top EDTA tubes and thoroughly mixed.

Peripheral blood (four CPT tubes containing sodium citrate) will be obtained pre-treatment and post-treatment with ZD6474 and coded samples will be used for analysis of angiogenesis markers such as circulating endothelial cells (CEC) and circulating endothelial progenitor cells (CEP). The time points may vary as the optimal time vis a vis treatment needs to be empirically determined. Four CPT tubes containing sodium citrate (blue-black speckled top tubes) of peripheral blood will be sent to [name]'s laboratory in the Medical Oncology Branch, CCR, NCI. The CEC and CEP analysis will be performed using multiparameter flow cytometry, and may include ancillary studies such as real-time RT-PCR analysis of gene expression and *in vitro* endothelial cell culture. These studies are exploratory and intended to evaluate the utility of CECs and CEPs as surrogates for inhibition of angiogenesis following administration of ZD6474.

Although there is no universally accepted surrogate for angiogenesis inhibition, evaluation of CECs and CEPs have been proposed and validated by several groups (41-46). [name] lab has collaborated with other groups ([name], MD Anderson Cancer Center, and the Angiogenesis Core at the Beth Israel and Deaconess Medical Center) to standardize flow cytometric analyses of peripheral blood for evaluation of CEC/CEP. For this analysis, peripheral blood is drawn into 4 CPT citrate tubes. Mononuclear cells are isolated by centrifugation, washed with PBS, and FcR solution (Miltenyi) is added to block non-specific binding. Although the antibodies and fluorochromes used may vary, for identification of CECs and CEPs, cells are typically stained with FITC- conjugated anti-CD31, PerCP-conjugated anti-CD45, APC-conjugated anti-CD133, Hoechst 33258 and PE-conjugated CD146 and analysed on an LSR II flow cytometer (BD Biosciences), using LSR II-equipped digital data acquisition and FlowJo cytometric data analysis software. The CEC and CEP cell concentrations are calculated as a percentage of the total number of mononuclear cells or as the number of cells/microliter of whole blood after an evaluation of a minimum of 10^5 cellular events, and preferably 10^6 cellular events. CEC cells are defined by the co-expression, or absence of expression on a single cell of the following parameters: CD45-, CD31+, CD133- and CD146+, Hoechst 33258 (viable CEC) or CD45-, CD31+, CD133- and CD146+, Hoechst 33258+ (nonviable CEC). CEP cells are defined by the co-expression, or absence of expression on a single cell of the following parameters: CD45- or dim, CD31+, CD133+ and CD146-, Hoechst 33258- (viable CEP) or CD45- or dim, CD31+, CD133+ and CD146-, Hoechst 33258+ (nonviable CEP).

The outcome measures will be the number of CEC and CEP per 10^6 mononuclear cells or per microliter of peripheral blood, analyzed in samples taken before and after treatment. These numbers will then be examined for correlations with various parameters to assess their potential utility as surrogate biomarkers for drug activity, for establishing the optimal biologic dose, for patient stratification, and monitoring of therapy-related side effects.

In addition to multi-parameter flow CEC and CEP analysis, if there are a sufficient number of cells in the mononuclear fraction the cells will be set up *in vitro*, according to standard methods, for the endothelial progenitor cell colony forming assay (47, 48).

Correlative laboratory studies will be performed by investigators in the Urologic Oncology Branch and may involve collaboration with other NIH intramural investigators and/or Astra-Zeneca. Studies listed will be performed wherever possible and as permitted by sample and resource availability.

3.4.1 Collection, Storage, Use and Disposition of Human Specimens

3.4.1.1 Clinical Samples

Blood and urine samples for clinically relevant, non-research hematology, serum chemistry, urinalysis, and skin biopsy tissue will be prepared using standard procedures. Routine clinical analyses will be performed by the NIH Clinical Center central laboratories or NCI Pathology department. Samples will be processed and disposed according to standard laboratory procedure.

3.4.1.2 Storage and research use of research human specimens

- a) Sample Collection and Planned Research Studies-Research samples will be collected with a view to performing a variety of correlative/biomarker studies (as indicated in section 3.4).
- b) Sample Processing and Storage-Each patient research sample will be assigned a unique patient identifier and relevant sample characteristics (such as timing of sample collection, treatment cycle and day identifiers) will be recorded. The location of all samples will be carefully tracked in the database. All stored samples will be coded and no identifying patient information will be on placed on sample containers. Stored samples will be kept in freezers / refrigerators or secure containers located in the Urologic Oncology Branch research laboratories.
- c) Time frame for research studies- Samples will be stored until requested by an authorized researcher(s). All researchers are required to use the samples for research purposes associated with this trial (as per the NCI IRB approved protocol). Subjects will be given the option of consenting to future use of their research samples per the informed consent process with their option declared in the consent document. Samples from those patients who consent to this will be stored permanently. However, these samples will be used only for research studies on active NCI IRB approved protocols covered by a valid informed consent document. Samples will be destroyed at the completion of the study from those subjects who decline future use of their samples. Once primary research objectives for the protocol are achieved, intramural researchers can request access to remaining samples provided they have an IRB approved protocol and patient consent. Any unused samples must be returned to the UOB laboratories as appropriate. The PI will report destroyed samples to the IRB if samples become unsalvageable because of environmental factors (e.g. broken freezer or lack of dry ice in a shipping container) or if samples are destroyed because a patient withdraws consent. Samples will also be reported as lost if they are lost in transit between facilities or misplaced by a researcher. Any freezer problems, lost

samples or other problems associated with samples will be reported to the IRB, the NCI Clinical Director, and the office of the CCR, NCI.

3.5 STUDY EVALUATIONS AND SCHEDULE

3.5.1 Baseline Evaluation

These studies are intended to evaluate the presence and extent of nonrenal VHL-associated tumors and are not meant to determine eligibility. These studies may be performed before (as part of routine evaluation of VHL patients) or after eligibility assessment but no more than 3 months prior to study enrolment.

3.5.1.1 MRI of the spine to include: precontrast T-2 weighted surface coil images of the cervical and thoracic cord in the sagittal plane and post contrast (Gadolinium). CT imaging with and without contrast may be performed if MRI cannot be performed.

3.5.1.2 24 hour urine collection for catecholamine analysis when clinically indicated.

3.5.1.3 Standard complete audiogram to detect hearing loss and /or the presence of an ELST (endolymphatic sac tumor) in patients known or suspected to have these tumors.

3.5.1.4 CT examination of the internal auditory canal to evaluate for potential ELST in patients known or suspected to have these tumors.

3.5.1.5 For males, ultrasound of testicles with high resolution (5-7 MHz) transducer to evaluate the epididymis (0.75 hour scan time) when clinically indicated.

3.5.1.6 An ophthalmologic exam to screen for retinal angiomas.

3.5.1.7 Labs: serum erythropoietin, TSH, T3 and FreeT4, parathyroid function tests –spot urine phosphorous and spot urine creatinine, vitamin D 1-25, vitamin D 25-OH Serum PTH, FGF23 (1-2ml of plasma to be sent to [name]., Chief, Skeletal Clinical Studies Unit, CSDB, NIDCR)

3.5.2 On Study Evaluation

3.5.2.1 Before every cycle: Based on patient's status and schedule conflicts if deemed warranted pt's may be allowed to reschedule NIH protocol visits at the discretion of the PI, the patient and the research team.

- a. History and physical
- b. CBC, Chem 20, urinalysis and urine protein:creatinine ratio.
- c. ECG (A 12-lead ECG should be obtained on day 1, cycle 1 before the first dose of ZD6474 and repeated 4-8 hours after the first dose)
- d. Urine pregnancy test in women of childbearing potential

3.5.2.2 Every three cycles (Restaging cycles): Based on patient's status and schedule conflicts if deemed warranted pt's may be allowed to reschedule NIH protocol visits at the discretion of the PI, the patient and the research team.

- e. History and physical
- f. CBC, Chem 20
- g. Erythropoietin
- h. TSH, if elevated, T3 and Free T4, antiTPO and TSI and lipid panel
- i. Parathyroid function tests – serum PTH, spot urine phosphorus, spot urine creatinine, vitamin D 1-25, vitamin D 25-OH and FGF23 (1-2ml of plasma to be sent to [name]., Chief, Skeletal Clinical Studies Unit, CSDB, NIDCR)
- j. ECG
- k. Imaging studies: CT/MRI/Ultrasound evaluation of known/suspected disease sites (both renal and non-renal VHL associated lesions)
- l. Ophthalmologic evaluation in patients with baseline retinal angiomas
- m. Serum and Urine catecholamines in patients with baseline elevations

3.5.2.3 Weekly Monitoring

- n. 12 lead ECG for the first two cycles (within 4-8 hours after dose)
- o. Chem 20 for the first two cycles

3.5.2.4 Daily Monitoring

Blood Pressure- Patient will be asked to measure and record his blood pressure at least once a day and will be provided with a BP monitor. Patients will be instructed to record BP readings on a BP monitoring diary which will be provided and will be reviewed by the research nurse/PI/AI at each clinic visit. In addition, patients will call the UOB research team for readings above 150/100mm Hg and may be instructed to have elevated readings confirmed by a local health care provider.

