- QTc with Bazett's correction that is unmeasurable, or ≥ 480 msec on screening ECG. If a patient has QTc ≥ 480 msec on screening ECG, the screen ECG may be repeated twice (at least 24 hours apart). The average QTc from the three screening ECGs must be < 480 msec in order for the patient to be eligible for the study). Patients who are receiving a drug that has a risk of QTc prolongation (see [Appendix C](#), Group/Table 2) are excluded if QTc is ≥ 460 msec.
- Potassium concentration less than 4.0 mEq/L, calcium (ionized calcium or adjusted for albumin), or magnesium concentrations outside normal limits despite optimal supplementation/correction
- Left ventricular ejection fraction less than 45% measured by multiple gated acquisition scan (MUGA) or echocardiogram (ECHO)
- Hypertension not controlled by medical therapy (systolic blood pressure greater than 150 mmHg or diastolic blood pressure greater than 100 mmHg).
- Uncontrolled intercurrent illness including, but not limited to, ongoing or active infection, symptomatic congestive heart failure, unstable angina pectoris, cardiac arrhythmia, or psychiatric illness/social situations that would limit compliance with study requirements.
- Patient known to be HIV positive and requiring antiretroviral therapy
- Currently active diarrhea that may affect the ability of the patient to absorb ZD6474 or tolerate further diarrhea.
- Patients on therapeutic anticoagulation
- Patients with known bleeding disorders
- Pregnant women are excluded from this study because ZD6474 is an anti-angiogenic agent with the potential for teratogenic or abortifacient effects. Because there is an unknown but potential risk for adverse events in nursing infants secondary to treatment of the mother with ZD6474, breastfeeding should be discontinued if the mother is treated with ZD6474
- Any known hypersensitivity to ZD 6474 or other excipients of ZD6474

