3.3.3 QT prolongation

QT prolongation will be managed as follows:

Monitoring for QT prolongation

All patients on study will get a weekly 12 lead EKG for the first 2 cycles. Thereafter (in the absence of QT prolongation), a monthly ECG will be performed while the patient is on the study drug. The following algorithm will be used to monitor/manage QTc prolongation.

QTc prolongation is defined as

A single QTc value of ≥ 500 msec or an increase of ≥ 100 msec from baseline;

[figure not shown]
OR

Two QTc measurements where either of the following criteria are met for both QTc values (the second being the mean of 3 consecutive ECGs):

A QTc interval ≥ 500 msec but < 550 msec, **OR**
An increase of ≥ 60 msec, but < 100 msec, from baseline QTc to a QTc value ≥ 480 msec.
Management of Patients With QTc Prolongation

For a single QTc value of ≥ 500 msec or an increase of ≥ 100 msec from baseline, ZD6474 must be withheld. ECGs and electrolytes should be followed 3 times a week until QTc falls below 480 msec or baseline, whichever is higher. ZD6474 treatment may be resumed at a lower dose after the QTc recovers to < 480 msec or baseline.

For a QTc ≥ 500 ms but < 550 ms (grade 3 CTCAE v3.0) or ≥ 60 ms, but < 100 ms compared to baseline to a QTc value ≥ 480 msec, further ZD6474 dosing will be withheld and an ECG (in triplicate) obtained within 24 hours. If the repeat ECGs confirm a QTc ≥ 500 (mean calculated from 3 ECGs) or prolongation of ≥ 60 ms from baseline to a QTc ≥ 480 ms, QTc and electrolytes will be monitored three times a week until the QTc returns to baseline or below 480ms (whichever is higher); thereafter, ZD 6474 will be resumed at one lower dose level. If the repeat ECG reveals a QTc < 500 ms or a prolongation of < 60 ms from baseline, ZD6474 will be resumed at the current dose and an ECG repeated in 48 hours and thereafter as outlined in the study plan in the absence of QT prolongation (i.e., ≥ 500 ms or prolongation ≥ 60 ms from baseline to a value ≥ 480 msec). A second instance of QTc ≥ 500 ms (but < 550 ms) or QTc prolongation ≥ 60 ms from baseline to a value ≥ 480 msec will necessitate withholding drug until normalization of QTc and resumption thereafter at one lower dose level.

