7.2.2 Potential risks

Potential risks include the possible occurrence of any of a range of side effects that are listed in the pharmaceutical section and the consent document. The procedure for protecting against or minimizing risks will be to medically evaluate patients on a regular basis as described in sections 3 and 8.

The agent used in this trial is investigational. Experience with this agent to date suggests that this agent is associated with an acceptable toxicity profile. However, VHL patients may be at risk for

previously undefined or inadequately characterized complications from this agent owing to their unique clinical circumstances (e.g. potential risk of bleeding from cerebellar or spinal hemangioblastomas, unmasking or exacerbation of hypertension in patients with asymptomatic or occult pheochromocytomas etc.); these issues have been addressed in the consent document and in the appropriate sections of this protocols. The risk of delaying ‘standard of care’ therapy (resection of renal tumors ≥ 3 cm) in favor of an experimental therapy is considered to be minimal. The UOB has extensive experience with the management of VHL-associated renal tumors over the past 17 years. These tumors are slow growing tumors and often there is a 3-4 month time period between when surgery is recommended and is carried out. All patients enrolled on trial will be evaluated for a response of renal lesions following three cycles of therapy.

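### The home call level (above 150/100) omits Table 1 row A's diastolic-rise trigger, so at baseline diastolic 80 or below the early treatment that row A calls for can wait for the next BP check

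*Combined protocol and SAP*

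**What the plan says.** Three parts of the combined protocol and SAP bear on this.

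- **Home monitoring.** Patients measure BP at least daily and keep a diary that staff review at clinic visits. Section 3.5.2.4 gives the only numeric call level: "patients will call the UOB research team for readings above 150/100mm Hg". Section 3.3.4 also asks patients to "contact the UOB team for elevated readings", but gives no level and does not mention a change from baseline.
- **Treatment rule.** Row A of Table 1 (3.3.4) has three triggers joined by OR: systolic above 150, diastolic above 100, or "Increase of diastolic BP by ≥ 20 mmHg regardless of baseline BP". Any one of them calls for adding or increasing antihypertensive drugs, with the instruction "Maintain dose of ZD6474". Row A moves on to a hold only if BP cannot be brought below 150/100 within two weeks.
- **Who decides.** Section 3.3.4 states that "decisions regarding grading of hypertension and initiation/intensification of antihypertensive therapy will be driven by BP measurements performed by a health care professional".

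The Study Calendar (3.6) schedules vital signs on days 1 and 15 of cycle 1 and then on day 1 of each 28-day cycle, within a window of 3 days either side. For the QT programme, "All patients on study will get a weekly 12 lead EKG for the first 2 cycles", and 3.5.2.3 adds weekly chemistry over the same period. BP is not listed for those weekly contacts.

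**The concern.** Treatment rests on a professional reading, so between visits the home reading is the planned prompt to obtain one. The prompt reproduces two of row A's triggers and leaves out the one defined by change from baseline. Because that trigger applies whatever the baseline, it can be met at modest absolute pressures, which a fixed call level cannot detect in a patient who starts low.

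What is at stake is prompt treatment of mostly mild hypertension. A rise from baseline still has some meaning in this population: section 7.2.2 lists "unmasking or exacerbation of hypertension in patients with asymptomatic or occult pheochromocytomas" among the VHL-specific risks.

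**Working it through.** The plan gives no figure to reproduce here. The check is threshold arithmetic, a reading of the calendar, and an estimate of the burden of a wider call rule.

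**1. Readings that meet row A without reaching the call level.** Let b be baseline diastolic and d the home diastolic, in whole mmHg, with systolic at or below 150. Row A's rise trigger is d ≥ b + 20 (Table 1). The diastolic call level is d > 100 (3.5.2.4). Uncovered readings are b + 20 ≤ d ≤ 100, which exist only if b ≤ 80.

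The right-hand column supposes that patients also call at 140/90 or above. That is the level below which rows B and C resume drug; the plan does not say that it defines an elevated reading. Uncovered readings are then b + 20 ≤ d ≤ 89 with systolic below 140, which exist only if b ≤ 69.

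| Baseline diastolic | Uncovered, call only above 150/100 | Uncovered, call also at 140/90 or above |
|---|---|---|
| 60 | 80-100 | 80-89 |
| 65 | 85-100 | 85-89 |
| 69 | 89-100 | 89 only |
| 70 | 90-100 | none |
| 75 | 95-100 | none |
| 80 | 100 only | none |
| 81 or more | none | none |

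Example: baseline 112/62 and home readings of 132/84. The diastolic rise is 84 − 62 = 22, so row A's trigger is met, yet the reading is below both 150/100 and 140/90.

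**2. Time to the next scheduled vital signs (3.6, ignoring the visit window).** Study days 1, 15, 29, 57, 85 and 113 give gaps of 14, 14, 28, 28 and 28 days. The nominal wait is up to 14 days in cycle 1 and up to 28 days from cycle 2. If staff also take BP at the weekly ECG and chemistry contacts, it is up to 7 days in cycles 1-2 and 28 days from cycle 3.

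**3. What the delay can affect.** Every uncovered reading has systolic ≤ 150 and diastolic ≤ 100. Row A's control target is below 150/100, so all of them meet it except readings of exactly 150 or exactly 100. Row C requires more than 150 or more than 100 despite two weeks of therapy, and row B's numeric limits are more than 180 or more than 110. No uncovered reading meets a numeric criterion of row B or C.

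**4. Chance calls if the rise trigger is added.** Assumptions, none from the documents: day-to-day SD of home diastolic 5-8 mmHg, normally distributed, no true rise, one reading a day, and a baseline that is the mean of n = 3 home readings.

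Expected calls per 28 days = 28 × P(Z > t / (SD × √(1 + 1/n))).

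- Home baseline, t = 20: 0.007 at SD 5 and 0.43 at SD 8.
- Clinic baseline 5 mmHg below the home level (assumed), t = 15: 0.13 and 1.46.
- Clinic baseline 5 mmHg above the home level (assumed), t = 25: 0.0002 and 0.10. Here the rule would in effect wait for a 25 mmHg home rise.

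**The case against.** The strongest reply has four parts.

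- **A wider instruction exists.** The request to report elevated readings stands just above Table 1 and could be read in its light, which would make 150/100 a minimum and not the only prompt. This stands in part. It narrows the gap, but it sets no level and does not mention change from baseline. Even at 140/90 the gap remains for baseline diastolic of 69 or less.
- **The plan already treats these readings as controlled.** This stands, apart from exact boundary values, and it is the main reason that the point is minor. Such readings would also be acceptable at entry, where the exclusion is uncontrolled hypertension with "systolic blood pressure greater than 150 mmHg or diastolic blood pressure greater than 100 mmHg".
- **The split may be deliberate.** One fixed number is easy for patients, and staff can apply the baseline comparison at diary review. That is a reasonable design, but its price is the wait shown above, and a value written on the diary would be just as simple to follow.
- **Frequency is unknown.** Baseline pressures are not given. The phase I summary reports hypertension in 21% of patients, with an average rise of 5 mmHg in mean arterial pressure, which does not suggest that diastolic rises of 20 mmHg are common. This stands.

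A reader might infer that dangerous hypertension could go unreported while full-dose drug continues, or that the pheochromocytoma risk goes unwatched. The documents do not support either. Readings above 150/100 prompt a call, row B covers symptomatic hypertension at any value, and section 7.2.2 says that the VHL-specific risks are addressed in the consent document, which is not available here. Nor are the instructions printed on the diary.

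**Conclusion.** The point holds as a minor mismatch between two rules in the same plan: the home call level covers two of row A's three triggers. It can matter only at baseline diastolic of 80 or less, or 69 or less if patients also call at 140/90, and only for rises that stay within the ranges tabulated. What is delayed is the early antihypertensive treatment that row A asks for, nominally by up to 14 days in cycle 1 and 28 days from cycle 2, and by less in cycles 1-2 if BP is taken at the weekly contacts. Holds, dose reductions and the primary endpoint are unaffected.

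The ranges and intervals follow directly from the plan's text and its nominal visit days. How many patients would be affected cannot be derived.

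**What to change.** In 3.5.2.4, tell patients to call for systolic above 150, or diastolic above 100, or diastolic at or above their own baseline plus 20 mmHg, and write that last value on the BP diary. Measured against that baseline, this empties the uncovered range at every starting value. Keep professional confirmation before Table 1 is applied.

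Preferably define the baseline for calls as the mean of at least three pre-dose readings on the supplied home monitor, issued at screening, so that home readings are compared with a home value.

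The cost is one sentence, one diary entry, handing out the monitor before day 1, and a home baseline that sits alongside the professional readings used for Table 1. Chance calls would number about 0.01-0.4 per patient per 28-day cycle under the assumed SD of 5-8 mmHg. That range is wide because the SD is not known from the documents. Each such call leads at most to a confirmatory reading, since treatment still depends on a professional measurement.
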